## 7.9.      **Electrocardiography**

A 12-lead ECG will be recorded at the time points detailed in [Table 4](#) and [Table 5](#). All ECGs will be performed after at least 5-minute rest in a supine or semi-supine position. The investigator should review the ECG at day 1 and at screening (in case a screening visit is performed) to determine patient eligibility for the study and subsequent ECGs for the patient's continuation in the study. A qualified physician at a central diagnostic center will be interpreting the ECG.

The ECG types are defined as follows:

- A “standard ECG” is a “standard” 10-second 12-lead ECG.
- A “summary ECG” is a continuously recorded ECG of longer than 10 seconds. For a “summary ECG,” the minimal recommended duration is 2 minutes or longer, and the preferred duration is 5 minutes (as it provides the most robust result). If a “summary ECG” is less than 2 minutes, data will still be captured and analyzed to the extent possible.

The investigator should review the ECG at screening to determine patient eligibility for the study and subsequent ECGs for the patient's continuation in the study. All ECGs should be reviewed by the investigator for any clinically significant findings during the visit, and before the patient leaves the clinic. A qualified physician at Spaulding (the central diagnostic center) will interpret the ECG.

All ECG results outside of the reference ranges will be judged by the investigator as belonging to one of the following categories:

- abnormal and not clinically significant
- abnormal and clinically significant

Any ECG finding that is judged by the investigator as clinically significant will be considered an adverse event, recorded on the source documentation and in the CRF, and monitored as described in [Section 7.1.2](#).

The criteria for an abnormal post-baseline QTcF are a value  $>500$  msec or change from screening  $>60$  msec. If one of these criteria is met, the investigator must further evaluate the QTcF as follows:

- If a standard ECG is abnormal and meets the above protocol criteria:
  - A 5-minute summary ECG recording should be performed at the research site, and a repeat standard ECG is not required. The site should follow the process to have these ECGs read by Spaulding.
  - If a 5-minute summary ECG cannot be performed (for instance, if the patient is evaluated at a facility other than the research site, and the summary ECG is not available), the investigator should obtain 2 repeat standard ECGs and determine the average of these 3 post-screening QTcF values. The site should follow the process to have these ECGs read by Spaulding.

- The investigator should then compare the post-screening QTcF values to the pre-treatment QTcF values at screening. As noted above, the post-screening QTcF values will use either the average QTcF from the 3 post-screening standard ECGs or the QTcF from the summary ECG. The IMP must be stopped for any confirmed post-baseline QTcF average value >500 msec or average increase from screening >60 msec.

For COVID-19 updates, refer to [Appendix M](#).

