## 4.2. Patient Exclusion Criteria

Patients will not be randomized/enrolled in this study if they meet any of the following criteria:

- a. Patient has clinically significant depression at screening or day 1 of this study.
  - Note: Patients receiving antidepressant therapy may be enrolled if on a stable dose for at least 6 weeks before screening or day 1 (whichever comes first) and anticipated to remain stable (dose and frequency) within the study duration.
- b. Patient has a history of suicidal intent or related behaviors based on medical or psychiatric history or the C-SSRS at screening visit, if performed, or at the day 1 visit, as applicable according to the patient's age:
  - intent to act on suicidal ideation with a specific plan, irrespective of level of ambivalence, at the time of suicidal thought
  - suicidal preparatory acts or behavior
- c. Patient has a history of a previous actual, interrupted, or aborted suicide attempt based on medical or psychiatric history or the C-SSRS at screening visit, if performed, or at the day 1 visit, as applicable according to the patient's age.
- d. Patient has a first-degree relative who has completed suicide.
- e. Patient has received any of the following concomitant medications within the specified exclusionary windows from screening or day 1 (whichever comes first) of this study:
  - within 30 days: tetrabenazine or valbenazine
  - within 21 days: reserpine
  - within 14 days: levodopa, dopamine agonists, and monoamine oxidase inhibitors
- f. Patient has received treatment with stem cells, deep brain stimulation, transmagnetic stimulation, or transcranial direct current stimulation for treatment of abnormal movements or CP since the week 15 visit of Study TV50717-CNS-30080, or the patient is not in a stable clinical condition.
- g. Patient had a surgical procedure since the week 15 visit of Study TV50717-CNS-30080 or is anticipated to have a surgical procedure during the study that, in the opinion of the investigator, makes the patient unsuitable for the study.
- h. Patient has a severe mental disability or an unstable or serious medical illness (eg, epilepsy) that, in the opinion of the investigator, could jeopardize or would compromise the patient's ability to participate in this study.

- i. Patient has a QT interval (QTc) corrected for heart rate using Fridericia's formula (QTcF) value  $>450$  msec on 12-lead ECG at screening or day 1 (whichever comes first) of this study.

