### 4.3. Withdrawal Criteria and Procedures for the Patient

In accordance with the Declaration of Helsinki (in accordance with the applicable country's acceptance), each patient is free to withdraw from the IMP at any time. The investigator also has the right to withdraw a patient from the IMP in the event of intercurrent illness, adverse events, pregnancy (see Section 7.3), or change in concomitant treatment (see [Appendix H](#)); patient engages in alcohol or other substance abuse; patient or parent(s)/legally acceptable representative withdraws consent or requests discontinuation from the IMP; the sponsor requests withdrawal of the patient or other reasons concerning the health or well-being of the patient; or in the event of lack of cooperation.

If a patient experiences signs of suicidal ideation or behavior (Section 7.10), the investigator should consult with the medical monitor to determine whether the patient should continue in the study. If a patient reports any suicidal behavior that is an actual attempt as assessed in the children's C-SSRS, the patient will be evaluated immediately by the investigator, referred for psychiatric evaluation, and terminated from the study.

Patients are expected to participate in this study for its entire duration and perform the scheduled visits and procedures.

Patients will be discontinued from the study for the following situations:

- Laboratory evidence of diminished hepatic function, defined as an AST or ALT  $>2.5\times\text{ULN}$  and ALP or total bilirubin  $>2\times\text{ULN}$
- Patient develops neuroleptic malignant syndrome

If a post-treatment QTcF value  $>500$  msec or change from screening or day 1  $>60$  msec is found, the investigator should repeat the ECG assessment twice and then compare the last pre-treatment QTcF value to the average of the 3 post-treatment QTcF values. TEV-50717 must be stopped for any confirmed post-treatment QTcF average value  $>500$  msec or average increase from screening or day 1  $>60$  msec. In addition, a patient may be withdrawn from the study as described in Section 3.4, Section 3.5, and [Appendix C](#).

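### Protocol 4.3 and 7.9 impose the same mandatory QTcF stop but confirm it differently, so where a summary ECG is available the same patient can be stopped under one section and not under the other

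*Protocol*

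**What the plan says.** Both sections act on the same finding after treatment has started: a QTcF above 500 msec or a rise above 60 msec. Both then make stopping mandatory if the finding is confirmed. Section 4.3 says "TEV-50717 must be stopped for any confirmed post-treatment QTcF average value" exceeds the limit. Section 7.9 says "The IMP must be stopped for any confirmed post-baseline QTcF average value >500 msec or average increase from screening >60 msec".

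The confirmation steps differ:

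- **Protocol 4.3 (withdrawal criteria).** On an abnormal value, "the investigator should repeat the ECG assessment twice and then compare the last pre-treatment QTcF value to the average of the 3 post-treatment QTcF values". It mentions no summary ECG and does not refer to Section 7.9.
- **Protocol 7.9 (electrocardiography), summary ECG possible.** "A 5-minute summary ECG recording should be performed at the research site, and a repeat standard ECG is not required".
- **Protocol 7.9, summary ECG not possible.** Here "the investigator should obtain 2 repeat standard ECGs and determine the average of these 3 post-screening QTcF values". The section then states that "the post-screening QTcF values will use either the average QTcF from the 3 post-screening standard ECGs or the QTcF from the summary ECG".

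The reference for the 60 msec rise also differs. Section 4.3 allows screening or day 1, and Section 7.9 names screening only. SAP 8.9 sends the investigator to Protocol 7.9 for further evaluation. It defines a confirmed QTcF as the mean of up to three standard ECGs or a single summary ECG.

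**The concern.** The rule is meant to give one answer for one patient, and stopping is obligatory in a paediatric study. A site that opens the withdrawal section takes two more standard ECGs and averages three values. A site that opens the ECG section takes one summary recording and ignores the abnormal tracing. Nothing in the protocol says which section prevails.

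The effect on the data is secondary but real. ECG parameters are a safety endpoint under the primary objective. If sites follow different sections, the SAP's counts of confirmed QTcF prolongation mix two procedures.

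The reference wording is a smaller defect. Read literally, Section 7.9 measures the rise from an ECG that most entry routes do not schedule.

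**Working it through.** **Inputs.** The limits (above 500 msec, rise above 60 msec) and the two confirmation steps come from Protocol 4.3 and 7.9. Exclusion criterion i in Protocol 4.2 caps the baseline at 450 "msec on 12-lead ECG at screening or day 1 (whichever comes first) of this study". All individual readings below are assumed, because the documents give none.

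**Notation.** Let b be the baseline, T the triggering value and r the level of every later reading (both repeats and the summary). A patient is stopped when the deciding value exceeds L = min(500, b + 60). L is 500 only when b is 440 or more; below that it is b + 60.

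- Deciding value under 4.3: (T + 2r)/3
- Deciding value under 7.9 with a summary ECG: r

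**When they disagree.** (T + 2r)/3 > L exactly when r > L − (T − L)/2. So 4.3 stops and 7.9 does not when L − (T − L)/2 < r ≤ L. The band has width (T − L)/2: 2.5, 5, 10 or 15 msec when the trigger exceeds the limit by 5, 10, 20 or 30 msec.

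| b | T | r | L | Band for r | 4.3 value | 7.9 value |
|---|---|---|---|---|---|---|
| 445 | 510 | 496 | 500 | 495 to 500 | 1502/3 = 500.7, stop | 496 (+51), no stop |
| 420 | 490 | 476 | 480 | 475 to 480 | 1442/3 = 480.7 (+60.7), stop | 476 (+56), no stop |
| 400 | 480 | 455 | 460 | 450 to 460 | 1390/3 = 463.3 (+63.3), stop | 455 (+55), no stop |

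The 510/496 pair is discordant only for b from 436 to 450. Below 436, 496 − b exceeds 60 and both sections stop.

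**The reverse direction.** With one common r, 7.9 can never stop when 4.3 does not; that follows from the assumption. If the summary differs from the repeats, the reverse needs the summary to exceed the mean of the repeats by more than (T − L)/2. Example: trigger 502, repeats 497 and 496, summary 503. Section 4.3 gives 1495/3 = 498.3 (no stop) and 7.9 gives 503 (stop). In whole msec this holds for b of 439 or more, since 498.3 − b must not exceed 60.

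**How often, under assumed variability.** The documents give no ECG variability. I assumed independent normal errors, a standard-ECG SD of 8 to 12 msec and a summary-ECG SD of 0.3 to 0.6 times that. I applied the 500 msec criterion only, conditional on a first standard ECG above 500, with 1,000,000 draws per scenario before that condition.

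| True QTcF | Stop under 4.3 | Stop under 7.9 | Disagree |
|---|---|---|---|
| 490 | 8–23% | 0–8% | 9–27% |
| 495 | 33–45% | 2–24% | 34–47% |
| 500 | 69–70% | 50% | 50% |
| 505 | 88–93% | 76–98% | 9–31% |

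These rates apply only to patients who have already triggered. They do not estimate how many will.

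**Reference ECG.** Protocol Table 4 and Appendix C 2.1 to 2.3 schedule one pre-treatment ECG per entry route:

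- 1 to <2 weeks after the parent study's week 15 visit: day 1
- 2 to ≤4 weeks, no clinically significant change: day 1
- 2 to ≤4 weeks, with such a change: screening only

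So the screening reference in 7.9 exists in one route of three. The intent can be inferred: 7.9 itself says "The investigator should review the ECG at day 1 and at screening (in case a screening visit is performed"), and SAP 4.2 takes the last value before the first dose as baseline.

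**The case against.** The strongest reply is that each section states a condition sufficient for stopping, and neither tells a site to continue if confirmation fails. Section 7.9 does not forbid repeat ECGs, so a site could take the summary and the repeats and stop if either rule is met. The investigator may also withdraw a patient for other health reasons. Section 7.9 is the dedicated and more detailed text, and SAP 8.9 points to it alone. The band is narrow, the readings are hypothetical, and the study is small (about 45 planned, 42 enrolled at Amendment 04). Manuals not available here may already tell sites what to do.

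Some of this stands. No frequency can be claimed, and site practice is unknown. Without a summary ECG, as may happen with home or local-clinic ECGs under Appendix M, both sections average three standard ECGs and only the reference wording differs. The SAP match to 7.9 is also approximate: its "up to 3" wording would accept fewer standard ECGs than the three that the fallback requires.

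It does not remove the conflict. A site that follows 7.9 as written does not obtain the repeats, so it cannot learn that the 4.3 condition was met. Greater detail is not a precedence clause, and a SAP does not instruct sites. Discretion to withdraw does not give a mandatory rule one meaning.

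**Conclusion.** The concern holds. Two current protocol sections attach the same mandatory stop to different confirmation procedures, and where a summary ECG is available they can give opposite results for one patient. That follows from the text and simple arithmetic. The size of the band rests on the later readings agreeing, and the simulated rates rest on the assumed SDs. The likelihood of any such case in this study is not known.

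This must be fixed, because a mandatory safety stop needs one meaning. That grading rests on the confirmation step alone; the reference wording is a secondary defect whose intent is recoverable. Neither procedure is judged right or wrong here.

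**What to change.** Reconcile Protocol 4.3 and 7.9 so that both state one confirmation procedure, including whether the triggering value counts in the deciding value. Both should name one reference ECG, worded so that it exists in all three entry routes from ECGs already scheduled. The choice of procedure belongs to the sponsor's clinicians. Then check SAP 8.9 against the reconciled text, including the number of standard ECGs needed for a confirmed value.

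As background only: the Amendment 04 summary of changes records that the repeat-twice paragraph was removed from 7.9. The same paragraph still stands in 4.3, which suggests how the two came apart.

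The cost is wording in an administrative letter or amendment and a notice to sites. It needs no new ECGs or visits.

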## 7.10. Assessment of Suicidality

TEV-50717 is considered to be central nervous system-active. In addition, there have been some reports of suicidal ideation or behavior as reported in the product label when it has been given to some patients with certain conditions. The sponsor considers it important to monitor for such events before and during this clinical study.

Some central nervous system-active IMPs may be associated with an increased risk of suicidal ideation or behavior when given to some patients with certain conditions. Although this IMP or other similar medicinal products in this class have not been shown to be associated with an increased risk of suicidal thinking or behavior when given to this study population, the sponsor considers it important to monitor for such events before or during this clinical study.

The study population being administered with TEV-50717 should be monitored appropriately and observed closely for suicidal ideation and behavior or any other unusual changes in behavior. Consideration should be given to discontinuing TEV-50717 in patients who experience signs of suicidal ideation or behavior.

Caregivers of patients being treated with TEV-50717 should be instructed to monitor patients for the emergence of unusual changes in behavior, as well as the emergence of suicidal ideation and behavior, and to report such symptoms immediately to the study investigator.

Day 1 assessment of suicidal ideation and behavior and treatment-emergent suicidal ideation and behavior will be assessed during the study using the children's C-SSRS described in Section [7.2](#).

Patients with a positive children's C-SSRS suicidal ideation score on either items 1 or 2 must be 1) discussed with the study medical monitor, 2) re-evaluated within 2 to 3 days in a clinic visit, and 3) treated according to the investigator's medical judgment. Consultation with a child/adolescent psychiatrist or licensed child/adolescent mental health provider is advised, followed by close ongoing monitoring.

If patients endorse or report a children's C-SSRS suicidal ideation score of 3, 4, or 5, the patients will be evaluated immediately by the investigator and referred for psychiatric evaluation. The medical monitor will be immediately consulted. If it is determined by the investigator, the medical monitor, and consulting psychiatrist that exposure to the IMP may have contributed to a change in children's C-SSRS and/or increased depressive symptoms, study medication will be immediately discontinued and the patient will be terminated from the study. In cases where it is determined that IMP did not contribute to changes in depression or suicidality, the investigator will consult with the medical monitor, consulting psychiatrist, and/or sponsor to determine whether the patient should continue in the study.

If patients report any suicidal behavior that is an actual attempt as assessed in the children's C-SSRS, they will be evaluated immediately by the investigator, referred for psychiatric evaluation, and terminated from the study.

If patients report any suicidal behavior that is interrupted, aborted, or preparatory as assessed in the children's C-SSRS, they will be evaluated immediately by the investigator and referred for psychiatric evaluation. In cases where it is determined in the psychiatric evaluation that IMP did not contribute to changes in suicidal behavior, the investigator will consult with the medical monitor, consulting psychiatrist, and/or sponsor to determine whether the patient should continue in the study.

## **7.11. Assessment of Depression**

Caregivers of patients are instructed to monitor the patients for any changes in or new onset of depressive symptoms and unusual changes in mood, cognition, or behavior, and to report such symptoms immediately to the investigator. Telephone contacts (with non-recording live video) and clinic visits also allow opportunities for the investigator to assess adverse events.

If a relevant change in status is identified, patients will be seen immediately for an unscheduled visit by the investigator and discussed with the medical monitor. The patient will be referred for further psychiatric evaluation if there is any suspicion of experiencing depression. The investigator will record these symptoms as an adverse event of depression. If it is determined by the investigator, after consultation with the medical monitor and consulting psychiatrist, that exposure to the IMP may have contributed to the adverse event of depression, the study medication will be immediately discontinued and the patient will be terminated from the study. Follow-up with a pediatric psychiatrist or licensed child/adolescent mental health provider will be arranged.

In cases where it is determined that IMP did not contribute to the adverse event of depression, the investigator will consult with the medical monitor and/or sponsor to determine whether the patient should continue in the study.

## **7.12. Concomitant Medication or Treatment**

Concomitant therapy or medication usage will be monitored throughout the study according to time points detailed in [Table 4](#) and [Table 5](#). Patients and/or caregivers will be instructed during the course of the study to notify the investigator if any new medication is prescribed/administered (other than TEV-50717) or there is any change in current medications, including over-the-counter medications. Any prescribed/administered medication should be reviewed with the investigator.

Patients may be included in this study if they are using cannabis or formulations or derivatives of cannabis in relatively stable amounts, for medical purposes (where applicable according to local regulation), under the guidance, supervision, or prescription of a clinician and anticipated to remain stable (dose and frequency) within the study duration. Patients who are either using cannabis or its derivatives or formulations or patients who have a positive drug screen for cannabis or its derivatives or formulations must be submitted to the medical monitor for consideration of participation in this study. If per the investigator's judgment, however, a patient does not meet the criteria for substance use disorder, a positive drug screen for cannabis or its

metabolites, without medical explanation, will be discussed on a case-by-case basis between the research site, the Medical Monitor, and the sponsor to determine the patient's eligibility, based on the information available. Patients should be advised that the recreational use of cannabis or its derivatives or formulations should be avoided during this study.

Medications that are allowed, provided that conditions outlined in the table are met, are shown in Appendix H, [Table 11](#). Certain considerations mentioned in the table require the review of the medical monitor. Changes to the allowed medications may be permitted in the context of this study if pre-approved by the medical monitor.

The medical monitor must be contacted if a patient is receiving (or has to begin or stop receiving during the study) a medication that is associated with QTc prolongation or that is a known strong CYP2D6 inhibitor. Prohibited medications that are associated with QTc prolongation are listed in Appendix H, [Table 12](#).

### **7.13. Methods and Time Points of Assessing, Recording, and Analyzing Safety Data**

All adverse events will be reviewed on a periodic basis by the clinical project physician/medical monitor according to the safety monitoring plan (eg, scheduled safety reviews for TEV-50717) as preliminary safety databases become available.

Methods and time points of assessing safety data are discussed in Section [3.5](#). Procedures for recording safety data are discussed in [Appendix K](#), and methods of analyses are discussed in Section [9.6](#).

**8. ASSESSMENT OF  
PHARMACOKINETICS/PHARMACODYNAMICS AND  
PHARMACOGENETICS**

